The aims of the study are to (1) Determine the feasibility and acceptability of Wits Workout among 120 intervention group recipients who receive the program at 8 locations in Illinois; and (2) Use a randomized trial to examine the preliminary efficacy of Wits Workout on changes in the primary outcomes of cognitive functioning, and secondary outcomes of self-efficacy, socialization, sleep, stress and physical activity levels following the 12-week intervention (3 months) and explore maintenance effects at 6 months (3-months post-intervention) compared to a waitlist control.

Hypotheses: At three and six-month posttests, intervention participants compared to controls will differentially improve with respect to (1) PROMIS^{6,7} self-reported cognitive function measures; (2) scores on the Telephone Interview for Cognitive Screening (TICS); and (3) self-efficacy, socialization, sleep, stress and physical activity levels.

Research Design

We propose to conduct a two-arm randomized controlled trial with a treatment (workshop) group and wait-list control group. We will assess participant outcomes at baseline, immediately post-workshop (3-months) and at 6-months to assess maintenance of treatment effects.

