baseline assessment is completed, participants will be randomized into two groups by a member of the research team. The treatment group will receive the 12-week workshop and the waitlist control group will receive the treatment after the six-month posttest is complete (see Figure 1). The first posttest and TICS will be administered by a member of the research team to both the workshop and control groups immediately following the end of the 12-week program (3 months). The 6-month follow-up assessment and TICS will be administered 3 months after the end of the program to both the workshop and control groups by a member of the research team. Reminders to complete the survey will be sent by a research team member by email and/or phone. Participants will be provided a \$20 gift card upon completion of each survey that will be administered by a research assistant. A "reunion" event will take place three months after the last *Wits Workout* session for the workshop group only. The reunion will give participants an opportunity to reconnect informally and it will enable the research team to conduct the follow-up focus groups. Qualitative methods are particularly well suited for the assessment of simulated changes in behavior and will provide us richer detail than the surveys alone¹⁶.

Power Analysis and Sample Size Estimation. In the cognition literature, a 1-3 point decrease in the Mini Mental State Exam score has been shown to be indicative of a meaningful decline. Our primary outcome, cognitive functioning, will be assessed using the TICS -- a telephone version of Mini Mental State Exam which is administered in person. Both measures correlate highly.^{9,10} Among older adults with normal cognition, which is our target sample for this trial, an effect size of 0.29 was considered clinically meaningful.¹¹ With this more conservative effect size of .20, an alpha of .05/6 = 0.008 9adjusted for multiple outcome measures and comparisons across rural and urban samples), for 3 time points (0-12-24 weeks), power set to .80, and an estimated correlation of .50 among measures, we need a total of 208 participants. Accounting for ~15% attrition, we will target to recruit a total of 240 participants for this trial. **Data Analysis**

Quantitative data. We will conduct 3x2 repeated measures ANOVAs to examine time (pre vs. post vs. follow-up),

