group (intervention vs. waitlist control), and interaction effects. The quantitative measures that will be evaluated using this statistical model include measures of social satisfaction and support, perceived well-being and quality of life, physical activity and exercise, self-efficacy, and the cognitive functioning scores. Covariates such as demographics [age, biological sex, geographic location (rural vs. urban)], and attendance to the Wits Workout program will be accounted for in the analyses. As a secondary analysis, we will also examine correlations between the demographic characteristics and the study outcomes. Drs. [name] and [name] have experience in analyzing similar large datasets from randomized controlled trials using these analysis strategies.

Qualitative data. [name] will conduct the focus groups using a guide to facilitate the discussion. The guide will include nine questions that will provide more in-depth detail about outcomes experienced by the participants (i.e. *In what ways did participating in Wits Workout impact your health behaviors?*) as well as questions that will provide details about their perception of the program (i.e. *What suggestions do you have to improve the program?*). We will audiotape and transcribe the focus groups. Three research team members will review all transcripts to develop an initial code book. We will then apply the codebook to a subsample of the transcripts individually then meet to discuss any areas where we are not coding consistently and adjust the codebook accordingly. We will then apply the same technique to another subsample of transcripts. Once we are certain that coding is consistent and the codebook is finalized, [name] will code the transcripts using NVivo QSR qualitative software. She will use an inductive thematic analysis process to analyze the data. Themes will be discussed and finalized with the research team.

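### The power paragraph names neither the effect-size metric nor the effect powered; 208 matches a group main effect at f = 0.20, while the group-by-time hypothesis reaches 80% power only at about 0.46 SD

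*Combined protocol and SAP*

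**What the plan says.** The Power Analysis and Sample Size Estimation paragraph first states that, in older adults with normal cognition, "an effect size of 0.29 was considered clinically meaningful". It then continues: "With this more conservative effect size of .20, an alpha of .05/6 = 0.008". The other inputs are three time points, power .80 and a correlation of .50 among measures. The result is that "we need a total of 208 participants", raised to 240 for about 15% attrition. Neither 0.29 nor .20 is given a metric, and no ANOVA effect is named as the one powered.

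Three other places bear on this:

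- **Overall Aims, Hypotheses:** "At three and six-month posttests, intervention participants compared to controls will differentially improve".
- **Data Analysis, Quantitative data:** the 3x2 ANOVA examines time, "group (intervention vs. waitlist control), and interaction effects". None is singled out.
- **Procedures:** once the "baseline assessment is completed, participants will be randomized into two groups".

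**The concern.** An effect size of 0.20 means very different things as a standardised mean difference d, as Cohen's f for a group main effect, or as f for an interaction. With metric and effect both unstated, a reader will naturally take the paragraph to promise 80% power for the stated hypothesis at an effect smaller than 0.29.

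The hypothesis is that the groups change differently from baseline, which is the group-by-time interaction. The group main effect is a different quantity, because it averages the group difference over all three visits, baseline included. Randomisation follows baseline, so the expected baseline difference is zero and dilutes that average.

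If 208 was derived for the main effect, the effect the trial can detect on its own hypothesis is not the one stated. A null result could then be misread as ruling out an effect near 0.29.

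**Working it through.** **Inputs from the plan.** Two equal groups (120 and 120), m = 3 time points, correlation r = 0.50, power 0.80, alpha .05/6 (printed as 0.008; 0.00833 unrounded), stated N = 208. With 15% lost, 240 × 0.85 = 204 are analysed. Assumed here: F tests, compound symmetry, no covariate adjustment and no clustering.

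**Step 1: reproduce 208.** Noncentral F, even N.

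- Group main effect: λ = f²·N·m / (1 + (m − 1)r), df 1 and N − 2.
- Group-by-time: λ = f²·N·m / (1 − r), df 2 and 2(N − 2).

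For the main effect with f = 0.20 and N = 208, λ = 0.04 × 208 × 3 / 2 = 12.48. Power at alpha 0.008 is 80.2%. At N = 206 it is 79.8%, so 208 is the smallest even N. With unrounded 0.05/6 the answer is 206.

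| Reading (alpha 0.008) | N for 80% power |
|---|---|
| Main effect, f = 0.20 | 208 |
| Main effect, f = 0.10 | 818 |
| Group-by-time, f = 0.20 | 64 |
| Group-by-time, f = 0.10 | 244 |

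**Step 2: what f = 0.20 on the main effect requires.** With two equal groups f = d/2, so f = 0.20 is a difference of 0.40 SD averaged over three visits. With differences (0, d, d) at baseline, 3 and 6 months, the average is 2d/3. Setting 2d/3 = 0.40 gives d = 0.60 SD at both posttests. Solving exactly at alpha 0.05/6 gives 0.596 SD (208 analysed) or 0.602 SD (204).

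**Step 3: power for the stated hypothesis.** For a group-difference profile p in SD units, with n = N/2 per arm, λ = (n/2)·Σ(p_j − p̄)² / (1 − r). For (0, d, d), the sum of squares is 2d²/3. At N = 208, λ = 52 × (2d²/3) / 0.5 = 69.33d². Alpha is 0.05/6.

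| Equal effect at both posttests | λ at 208 | Power, 208 analysed | Power, 204 analysed |
|---|---|---|---|
| 0.20 SD | 2.77 | 11% | 11% |
| 0.29 SD | 5.83 | 31% | 30% |
| 0.40 SD | 11.09 | 65% | 63% |

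Power reaches 80% at 0.458 SD with 208 analysed and at 0.462 SD with 204. Simulating the 3x2 ANOVA with 208 analysed (10,000 runs per setting) gave group-by-time power of 0.110, 0.303, 0.641 and 0.804 at 0.20, 0.29, 0.40 and 0.46 SD, and main-effect power of 0.801 at 0.60 SD.

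**Step 4: sensitivity at 204 analysed (effect for 80% power).**

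- r = 0.30: 0.547 SD.
- r = 0.70: 0.358 SD.
- r = 0.50, half the effect remaining at 6 months: 0.534 SD at 3 months.

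**Step 5: the reading of .20 as an interaction f.** For (0, d, d), f = d/√18, so f = 0.20 is d = 0.20 × 4.243 = 0.85 SD at both posttests. Power at 208 would exceed 99.9%, but 64 participants would suffice and 208 would be unexplained.

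**Step 6: is .20 the more conservative value?** If 0.29 and .20 are on the same scale, yes. If 0.29 is a d and .20 was used as an f (d = 0.40), no. The text does not allow a choice.

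**The case against.** The main-effect origin of 208 is an inference. The plan names no software and no convention, and the source behind 0.29 is not available here. The figure of 64 for an interaction f of 0.20 depends on the noncentrality convention; others give 124, 184 or 364. This stands as a caution, but none of these values is 208.

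The 0.46 SD is one scenario. The aims speak of exploring maintenance at 6 months and do not assume equal effects at the two posttests. One-degree-of-freedom contrasts at 208 analysed would detect 0.42 SD (mean of both posttests minus baseline) or 0.48 SD (change at one posttest). Adjusting the mean of the two posttests for baseline would detect about 0.34 SD, but that is not the planned analysis. It follows that 0.46 must be printed with its assumptions. None of these alternatives comes down to 0.29 SD.

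The intervention is delivered in group workshops, and the calculation ignores clustering. The documents give no intraclass correlation. Clustering is a separate matter, and it would only make the detectable effect larger.

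Finally, the aims are feasibility and preliminary efficacy, the interaction is already among the planned tests, and the remedy is a rewording. All true. The paragraph nevertheless fixes N by an explicit 80% power claim, and no reading tried makes 208 the number needed for group-by-time at .20.

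**Conclusion.** The concern holds. The metric and the powered effect are missing from the text. The stated inputs give 208 only for a between-group main effect at f = 0.20 and alpha 0.008, among the readings tried, and that is not the effect in the hypothesis.

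At the plan's own correlation and alpha, group-by-time power stays below 80% for any equal posttest effect up to 0.40 SD. The detectable effect is about 0.46 SD, with a range at 204 analysed of 0.358 to 0.547 SD over the correlations and effect patterns examined. The central figure assumes r = 0.50, compound symmetry, an equal effect at 3 and 6 months, and neither covariate adjustment nor clustering. This must be corrected, because the paragraph is the plan's only statistical justification for its sample size.

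**What to change.** Keep N unchanged and rewrite the power paragraph:

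1. State the metric of both 0.29 and .20, and record which calculation produced 208.
2. Name group-by-time as the effect to which the power statement applies, to match the Hypotheses.
3. Replace the 80% claim at .20 with the detectable effect of the planned 3x2 interaction at alpha 0.05/6 and r = 0.50: about 0.46 SD at both posttests (0.458 with 208 analysed, 0.462 with 204). Give the assumptions and the range beside it, and present it as what a fixed N can detect, not as the derivation of N.
4. Call .20 more conservative only if both values are on the same scale.

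The cost is one reworded paragraph, with no extra participants and no change to the planned ANOVA. The downside is that the stated detectable effect becomes less favourable.

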Qualitative Outcomes. We will conduct focus groups with participants 3 months after the conclusion of the workshops to learn more about the impact of the workshop on participant's health behaviors and their thoughts about how the program was delivered and evaluated.

[figure not shown]
Outcome Measures. We will examine the effects of participation in Wits Workout on the primary outcome of cognitive functioning and secondary outcomes of improved social satisfaction, self-efficacy, quality of life and sleep, reduced stress, and increased physical activity using the following measurements: Cognitive functioning will be assessed using the PROMIS Cognitive Function- Short Form 8a^{6,7} and the Telephone Interview for Cognitive Status (TICS). ^{8,9} TICS is a brief, standardized test of cognitive functioning designed to be measured over the telephone. Social-satisfaction will be assessed using the Cutrona Social Provisions Scale¹⁰. Self-efficacy will be assessed using the PROMIS Item Bank v1.0 - General Self-Efficacy. ⁶ Sleep will be assessed using the Pittsburg Sleep Quality Index (PSQI).¹³ Stress will be assessed using the Perceived Stress Scale.¹⁴ Physical activity will be assessed using the Physical Activity Scale for the Elderly (PASE).¹⁵

Participant inclusion/exclusion criteria: 1) age 50+; 2) English speaking /understands English; 3) No self-reported serious mental illness or diagnosis of Alzheimer's or other dementia related disease, and a score of 27 or higher on the TICS cognitive assessment during the screening call.

Procedures

Participants will be recruited through UI Extension utilizing community partners, the Extension website, Extension newsletters, and multiple media outlets, including news releases, fliers, and social media. Upon registering for the program, participants will be contacted and invited to take part in the research study. Those interested will be screened

for inclusion into the study with a brief telephone interview which includes the TICS assessment. Participants who are eligible will be sent a consent form and baseline assessment. University of Illinois at Chicago will provide institutional review board approval. All survey assessments will be administered online unless a participant is unable to complete the survey online in which case s/he will be offered the opportunity to take the survey via phone with a researcher or to receive a paper copy with a selfaddressed, stamped return envelope. Once the

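### The sample-size alpha of .05/6 cannot be traced to the planned tests, and the plan does not fix which test decides the primary outcome

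*Combined protocol and SAP*

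**What the plan says.** **Alpha.** Power Analysis and Sample Size Estimation sets "an alpha of .05/6 = 0.008 9adjusted for multiple outcome measures and comparisons across rural and urban samples" (the stray 9 appears to be an opening bracket). It does not list the six tests. The other inputs are "With this more conservative effect size of .20", "power set to .80", three time points and a correlation of .50. They lead to 208 participants, raised to 240 for about 15% attrition.

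**Analysis.** Data Analysis plans 3x2 repeated measures ANOVAs for each measure and looks at time, group and interaction effects. Location appears once, in the covariate list ("geographic location (rural vs. urban"). No rural or urban test, significance level or multiplicity rule is given.

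**Primary outcome.** Outcome Measures states "Cognitive functioning will be assessed using the PROMIS Cognitive Function- Short Form 8a" and adds TICS; the Hypotheses also list both. The power section states "Our primary outcome, cognitive functioning, will be assessed using the TICS" and does not mention PROMIS. Outcome Measures names seven instruments in all: the two cognitive ones plus social provisions, self-efficacy, sleep, stress and physical activity.

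**Visit.** Overall Aims will "explore maintenance effects at 6 months", while the Hypotheses read "At three and six-month posttests, intervention participants compared to controls will differentially improve".

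**The concern.** A multiplicity divisor has meaning only if a reader can list the tests it counts. This one is said to cover rural/urban comparisons that the analysis section does not contain, and it is not carried into that section.

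The more serious matter is the primary conclusion. Two cognitive instruments, two post-baseline visits and more than one ANOVA effect are available, no threshold is stated, and nothing says which result counts. A positive result on any one of them could be reported as the primary finding, and the plan gives no basis for disputing it.

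**Working it through.** **1. Reproduce the plan's N.** Inputs from the power section: effect size .20 (metric not stated, read here as Cohen's f), m = 3 visits, correlation rho = .50, alpha .008. For the between-group main effect in a two-group repeated measures ANOVA:

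- lambda = f² × N × m / (1 + (m − 1) × rho) = .04 × 208 × 3 / 2 = 12.48, with 1 and 206 degrees of freedom.
- Power = 80.2%. N = 206 gives 79.8%, so 208 is the smallest even total.
- With alpha unrounded at .00833, N = 206.

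Other readings at .008 do not give 208. The group-by-time interaction needs 64 or 364, depending on the noncentrality convention. A two-sample comparison at a standardised difference of .20 needs 1,222. So 208 is the group main effect.

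**2. What that test measures.** The group main effect compares the arms on the mean of all three visits. With two equal groups, f = .20 is a difference of 2 × .20 = .40 SD in that mean. Randomisation makes the expected baseline difference zero. A constant post-baseline difference D therefore contributes (0 + D + D)/3 = 2D/3, and 2D/3 = .40 requires D = .60 SD at both later visits. The hypothesis of differential improvement concerns change from baseline by arm, which is a different effect.

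**3. Try to find six tests.**

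| Reading | Count | Fits the stated rationale? | Fits Data Analysis? |
|---|---|---|---|
| Six domains in the second aim | 6 | No, nothing left for rural/urban | Partly; sleep and stress are not named there |
| Two cognitive scores plus the four other groups in Data Analysis | 6 | No, nothing left for rural/urban | Yes |
| Two cognitive measures × (all, rural, urban) | 6 | Yes | No, four of the six are not specified |
| Seven named instruments | 7 | No | Partly; sleep and stress are not named there |

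No reading fits both sections.

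**4. Family-wise error if .008 were applied to each test**, using 1 − (1 − .008)^k for independent tests:

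- k = 2: 1.6%
- k = 6: 4.7%
- k = 7: 5.5%

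Outcomes on the same people will be correlated. At assumed common correlations of .3 and .5, simulation of seven two-sided tests gives about 5.1% and 4.5%. The gap at seven is small.

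Because Data Analysis states no level, the opposite case is also open. Two cognitive tests each at .05, with either one counting as success, give 1 − .95² = 9.75% if independent.

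**5. Power for a 3-month group difference** at N = 208 and alpha .025 (the first Holm step for two tests), with f = .20, that is .40 SD:

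- Unadjusted: noncentrality = .40 × √(208/4) = 2.884, critical t = 2.258, power about 73%.
- Baseline-adjusted: residual SD factor √(1 − .50²) = .866, noncentrality = 2.884/.866 = 3.331, power about 86%.

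If .20 were instead a standardised mean difference, the unadjusted noncentrality would be 1.442 and power about 21%.

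**The case against.** The case on the other side is substantial, and much of it stands.

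- **.008 is only a sample-size input.** The plan never calls it the decision threshold, so it cannot be faulted as a failing threshold. This stands. The gap is that no threshold is stated.
- **Six can be counted.** With a six-test family the error rate is at or below 5%. This stands too, so a reader who infers that the divisor must either lose error control or waste power goes further than the text allows.
- **The secondaries are labelled secondary, and the aim is preliminary efficacy.** Strict control across all seven instruments is not obligatory, and the excess at seven is trivial or absent once correlation is allowed for. This stands for the secondaries but does not settle the primary.
- **The aims describe 6 months as exploratory.** This eases the conflict over visits but does not remove it, because the Hypotheses claim improvement at both.

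Two stronger inferences are tempting. One is that the error rate roughly doubles because every instrument is tested in both rural and urban samples. The documents specify no such tests. The other is that relaxing alpha to .025 raises power to 89.8%. That figure belongs to the three-visit main effect, not to a 3-month contrast.

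**Conclusion.** The concern holds as a matter of specification. The divisor cannot be traced to the planned tests, its rural/urban rationale has no counterpart in the analysis, and no alpha or multiplicity rule reaches Data Analysis. The primary test is left open by instrument, visit and effect, and this matters more than the divisor because it bears on the trial's main conclusion whichever way six is counted.

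The size cannot be put as one error rate, because the procedure is not defined. It depends on which tests count and at what level, as the illustrations show. The N of 208 is not wrong on its own inputs, but it powers a visit-averaged group effect rather than the hypothesised differential change. The documents do not show that error control is lost.

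The power figures assume that .20 is Cohen's f (the reading that reproduces 208), a correlation of .50, two-sided tests and 208 evaluable participants.

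**What to change.** In Data Analysis:

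1. Name two primary tests: the baseline-adjusted group difference at 3 months on TICS and on PROMIS Cognitive Function 8a, with Holm at overall two-sided .05. Align the aims, hypotheses and power section with this.
2. Make the 6-month contrasts and the other five instruments secondary, reported with confidence intervals.
3. Remove rural/urban from the divisor and report one exploratory group-by-location interaction. If confirmatory rural and urban tests are wanted, specify them, count them in the divisor and restate the power.
4. Restate the power for the chosen contrast, and say whether .20 is Cohen's f or a standardised mean difference. On the first reading, 208 participants give about 86% at .025 with baseline adjustment, against about 73% without it.

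The change is to wording only and needs no new participants or data. The cost is that secondary and 6-month results no longer carry a confirmatory claim.

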Intervention. Wits Workout will take place over 12 weeks, one hour per week. The training will be delivered by 5 UI Extension faculty educators who were trained by the Extension faculty educators who developed the program. Each week includes a themed module with four activities and a training component featuring educational topics such as a) exercising regularly; c) engaging the brain with new and intellectually stimulating challenges; d) participating in social activities; e) getting enough sleep; and f) reducing stress. The workshop will be offered in-person in 8 areas with a target of 20 attendees per urban workshop and 12 attendees per rural workshop for a total of 120 workshop participants. The waitlist control participants (n=120) will be offered the workshop after the 6-month study period is completed. All COVID safety requirements will be in place at the workshop sites. A fidelity assessment tool will be developed by the research team and implemented at all program sites. All Wits Workout leaders will be observed teaching two sessions of the program by one of the study investigators. After the first observation occurs, the fidelity evaluator will debrief with the leader and the evaluator will follow up with a written evaluation that includes strengths, areas of improvement (including ways in which they adhered and/or strayed from the program content and facilitation techniques outlined in the Wits Workout Leader's Guide), and suggestions for increasing fidelity in their teaching. A second observation will occur within the several weeks of the first observation with the goal of continuous process improvement from the first

to the second evaluation. UI faculty educators leading the workshops will record attendance over the 12 weeks and report to the investigative team. Attrition as well as completion rates will be documented based on workshop attendance.

Sample. We will offer Wits Workout to a minimum of 240 older adults (120 treatment and 120 delayed treatment controls) in three urban and five rural areas of Illinois (see

Location	Urban/Rural	Numbers	Waitlist
Chicago Area	Urban	20	20
Chicago Area	Urban	20	20
Champaign	Urban	20	20
St. Joe/Paxton	Rural	12	12
Sterling	Rural	12	12
Mattoon	Rural	12	12
Macomb	Rural	12	12
Marion	Rural	12	12
Total Participants		120	120

Table 1).

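### Recruiting 240 falls slightly short of the stated attrition allowance: a 15% loss leaves 204, not the 208 required, and 240 covers at most about 13%

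*Combined protocol and SAP*

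**What the plan says.** The section Power Analysis and Sample Size Estimation gives these inputs: "With this more conservative effect size of .20", "an alpha of .05/6 = 0.008", "power set to .80", three measurements at 0, 12 and 24 weeks, and a correlation of 0.50 between measurements. It concludes "we need a total of 208 participants" and continues "Accounting for ~15% attrition, we will target to recruit a total of 240 participants for this trial".

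The Sample paragraph under Research Design repeats the 240 as a lower bound: "We will offer Wits Workout to a minimum of 240 older adults (120 treatment and 120 delayed treatment controls", the bracket closing there. Table 1 lists three urban sites at 20 and five rural sites at 12, for workshop and waitlist alike. The Intervention paragraph calls the site numbers targets. It also says that attrition and completion will be documented from workshop attendance.

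The plan does not state the formula that takes 208 to 240, a larger recruitment target, or a rule for replacing people who withdraw.

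**The concern.** An attrition rate applies to the people recruited, so the check is whether 85% of 240 is at least 208. It is not. The sample-size paragraph therefore promises a retained number that its own attrition figure does not deliver.

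What is at stake is modest. At the planned rate of loss the trial would finish a few participants below its stated requirement, and power would sit just under the 80% the plan sets. A reader who takes 15% as the tolerable loss would accept 36 losses (240 × 0.15), where the stated requirement leaves room for 32.

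**Working it through.** **Inputs**, all from Power Analysis and Sample Size Estimation unless noted: required total 208; attrition about 15%; recruitment target 240, at 120 per arm (Sample, Table 1); effect size 0.20; alpha 0.05/6, written as 0.008; power 0.80; m = 3 measurements; r = 0.50. The analysis is a 3×2 repeated measures ANOVA (Data Analysis).

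**Step 1: reproduce the 208.** The plan names neither the effect-size metric nor the effect powered. I assume Cohen's f and the between-groups main effect, because that combination reproduces the figure. Power comes from the noncentral F distribution with 1 and N − 2 degrees of freedom and noncentrality

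λ = f² × N × m / (1 + (m − 1) × r).

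At N = 208, λ = 0.04 × 208 × 3 / 2 = 12.48. The smallest even N with at least 80% power is 208 at alpha 0.008, matching the plan. With the unrounded 0.05/6 = 0.00833 it is 206.

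**Step 2: reproduce the 240.** Two routes lead there:

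- 208 × 1.15 = 239.2, rounded up to 240.
- Table 1: 3 × 20 + 5 × 12 = 120 per arm, hence 240.

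**Step 3: apply the attrition rate to those recruited.**

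- Retained after a 15% loss: 240 × 0.85 = 204.
- Shortfall: 208 − 204 = 4.
- Largest tolerable loss: 240 − 208 = 32, and 32/240 = 13.3%.
- Number needed to keep 208 after a 15% loss: 208/0.85 = 244.7, so 245, or 246 for equal arms of 123.

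**Step 4: effect on power, under the step 1 assumption.** At N = 204, λ = 0.04 × 204 × 3 / 2 = 12.24.

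| Total N | Power, alpha 0.008 | Power, alpha 0.05/6 |
|---|---|---|
| 208 | 0.803 | 0.806 |
| 204 | 0.793 | 0.797 |

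The loss is about one percentage point. Steps 1 and 4 rest on the assumed metric and effect; step 3 does not.

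**The case against.** The strongest reply is that the gap lies within the precision of the inputs. The plan writes the rate as approximate, and 13.3% is not far from 15%. Part of the gap comes from rounding alpha: with 0.05/6 unrounded, the same calculation needs 206, and 240 then tolerates 34 losses (14.2%). Moving the assumed correlation from 0.50 to 0.48 brings power at 204 back to about 0.803. The trial also describes its aim as preliminary efficacy. All of this stands, and it is why the point is minor. It does not make the figures agree: the plan states 208, and 204 is below both 208 and 206.

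The plan also gives 240 as a minimum and the site numbers as targets, so enrolling five or six more would be compatible with the text. That is right, and a reader should not infer that Table 1 caps the trial at 120 per arm. But the text does not promise the extra enrolment, and the sample-size paragraph makes 240 the target.

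Three further inferences go beyond the documents:

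- *That the sponsor multiplied by 1.15 where division by 0.85 was needed.* The product fits, but so do the site numbers in Table 1, and no formula is given. The origin of 240 is unknown.
- *That the team will monitor retention against 15%.* No such threshold is set. The plan says only that attrition will be documented from attendance.
- *That the trial is shown to miss 80% power.* This depends on the assumed between-groups main effect. The hypotheses concern differential improvement, and under the same convention with f = 0.20 the group-by-time interaction would need only 64 participants.

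**Conclusion.** The point holds as a minor inconsistency in the stated figures. With 240 recruited, a 15% loss leaves 204, 4 below the stated 208, and the allowance that 240 actually provides is 32 participants, or 13.3%. This follows from the plan's own numbers alone.

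The power consequence is conditional. If the 208 was computed for the between-groups main effect with Cohen's f = 0.20, three measurements and r = 0.50, power at 204 is 79.3% to 79.7%, depending on whether alpha is rounded. That is just under the stated 80%. The documents do not support calling the trial materially underpowered on this account, and they do not show how the 240 was obtained.

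**What to change.** Keep 240 and correct the sentence in Power Analysis and Sample Size Estimation. Suggested wording:

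> Recruiting 240 allows for up to about 13% attrition (32 participants with missing outcomes across both arms) while retaining 208; at 15% attrition, 204 would remain.

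The 13% is a maximum loss and should not be labelled a retention target. Losses should be counted as missing outcomes in both arms, because workshop attendance cannot show them for the waitlist arm: "The waitlist control participants (n=120) will be offered the workshop after the 6-month study period is completed". If power at 204 is reported, name the effect and the effect-size metric in the same sentence; without them the figure cannot be checked.

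The cost is one sentence, with no added participants or sites. The only downside is that the stated attrition allowance becomes slightly less favourable. If the sponsor prefers to keep 15%, the matching target is 245, or 246 for equal arms.
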